## 2.3 Sample size and statistical power

In this study, we will use the generalized estimating equation (GEE) to detect the effectiveness of intervention in improving the quality of life. Since no previous research results are available for reference, we assume that the intervention in this study has a moderate effect. We set the effect amount as 0.25, the statistical power as 0.95, the alpha value as 0.05, and the number of repeated measurements as 3. The G\*power 3.1 statistical software shows that the required sample size was 178.

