## 2.4 Intervention group

At each visit of the research subjects to the plastic clinic, the research team records the attending prescriptions and patient education given by the medical team members and evaluates whether the research subjects and caregivers need additional mental support. Then, according to the

above evaluation and records, items of a designed patient education menu will be selected, and the selected patient education messages will be sent according to the transmission frequency and period proposed by the research subject

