## 2.7 Data collection

Before the study delivery, we will perform block randomization of four categories according to the statistical software (Sealed Envelope Ltd., 2022), with four as the block, and create label categories and case acceptance order according to the software allocation group, then putting the group name into the envelope. This study adopted categorical random allocation, with four categories: patients with neuropathic foot ulcers who received hemodialysis, patients with neuropathic foot ulcers who did not receive hemodialysis, patients without neuropathic foot ulcers who received hemodialysis, patients without neuropathic foot ulcers who did not receive hemodialysis.

After the research subjects agree to participate, the project leader will open envelopes to arrange their group location. Then, the data collection begins, including basic information on the research subjects, self-care behavior for diabetes, foot, and diabetic foot ulcers, self-efficacy in preventing and treating foot ulcers, quality of life, and wound measurement. Two post-tests (questionnaire interview and wound

assessment) will be conducted four and eight weeks after baseline data collection.

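### Section 2.7 does not say who makes the week-4 and week-8 assessments or keep them masked to allocation, which leaves wound area, and to a lesser degree the interview scales, open to assessor bias

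*Combined protocol and SAP*

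**What the plan says.** - **Order of events.** In section 2.7, once a patient agrees to take part, "the project leader will open envelopes to arrange their group location". Only then are the baseline questionnaires and the wound measurement done.
- **Follow-up.** The sentence in section 2.7 that begins "Two post-tests (questionnaire interview and wound" sets the same kinds of assessment at four and eight weeks. It is in the passive voice and names no assessor.
- **Contact with the intervention arm.** Under section 2.4, at each clinic visit "the research team records the attending prescriptions and patient education given by the medical team members". The team also judges whether more mental support is needed, and messages are chosen on that basis. Section 2.5 gives controls routine care only.
- **Outcomes.** Section 2.6.2 has wound size measured at baseline, four and eight weeks, with no method, device or measurer stated. Section 2.8 compares the proportions of wounds at least halved at four weeks by chi-square, and analyses self-care behaviour, self-efficacy and quality of life by GEE.
- **Masking.** No section supplied mentions masking, an independent assessor or a division of duties. The title pages are not part of that text and cannot be checked for such a statement.

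**The concern.** The project leader and the research team are the only people to whom the text assigns research tasks. The first knows every allocation, and the second would learn it through repeated contact with one arm. A site that followed the plan as written could let the same people trace the wounds and conduct the interviews.

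The wound outcome is sensitive to this. It is a ratio of two measured areas, made without a stated method and cut at a threshold, so a small shift in either area can move a patient across the line. The scales are completed by interview, and several ask about the behaviours that the messages promote, so an interviewer who knows the arm can prompt. Neither intention-to-treat analysis nor GEE corrects measurement error that differs between arms. Because allocation is revealed before baseline, the starting area, which is the denominator of the percentage reduction, is exposed too.

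**Working it through.** **Inputs from section 2.3.** "We set the effect amount as 0.25" (read as Cohen's f, so d = 2 × 0.25 = 0.50 for two groups), "the number of repeated measurements as 3", "the statistical power as 0.95", "the alpha value as 0.05", and the statement that "the required sample size was 178".

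**Assumptions.** The rest is not in the documents: 1:1 allocation without loss (178/2 = 89 per arm), a two-sided test, a correlation ρ between visits, control wound rates, and every bias size.

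**1. The plan's own figure.** For the between-groups effect in a repeated-measures ANOVA, λ = f²·N·m/(1 + (m − 1)ρ) with (1, N − 2) degrees of freedom. With ρ = 0.5 and N = 142, λ = 0.0625 × 142 × 3/2 = 13.31 and power is 0.952; at N = 140 power is 0.949. So 142 are needed, and 142/(1 − 0.20) = 177.5, rounded up to 178. Alternatively, ρ of about 0.77 with no dropout gives 178 directly. The figure can be reproduced, but only with an assumption that section 2.3 does not state. The rest of the check uses only N = 178.

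**2. Scale outcome, one visit, no true effect.** SE = √(2/89) = 0.150 SD, so a difference of 1.96 × 0.150 = 0.294 SD is significant. For a pure bias b, the probability of rejection is Φ(b/SE − 1.96) + Φ(−b/SE − 1.96).
- b = 0.1: Φ(−1.293) + Φ(−2.627) = 0.098 + 0.004 = 0.102.
- b = 0.2: Φ(−0.626) + Φ(−3.294) = 0.266.
- b = 0.3: 0.516.

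**3. Mean of both post-tests, ρ = 0.5.** The variance factor is (1 + 0.5)/2 = 0.75, so SE = √(0.75 × 2/89) = 0.130 and the critical difference is 0.254 SD. Biases of 0.1, 0.2 and 0.3 SD give 12%, 34% and 64%.

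**4. Wound outcome at four weeks.** Using z = (difference in proportions)/√(2p̄(1 − p̄)/89), this is the smallest excess of wounds classed as halved that gives z ≥ 1.96:

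| Assumed control rate | Halved, control v. intervention | Excess | z |
|---|---|---|---|
| 30% | 27 v. 40 | 13 (14.6 points) | 2.01 |
| 40% | 36 v. 50 | 14 (15.7 points) | 2.10 |
| 50% | 44 v. 57 | 13 (14.6 points) | 1.97 |
| 60% | 53 v. 66 | 13 (14.6 points) | 2.07 |

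A pure bias of 5, 10 or 15 points in the proportion gives about 10%, 27 to 29%, and 52 to 57% false positives over these control rates.

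**5. From measured area to proportion.** If percentage reduction were normal with mean 45 and SD 40 (one assumed case), the proportion at or above 50 would be 1 − Φ(5/40) = 0.45. A 5-point shift in measured reduction makes it 0.50, and a 10-point shift 0.55. For a single wound truly reduced by 45%, overstating the baseline area by 10% is enough: 1 − 0.55/1.10 = 0.50. This is why baseline matters as well as follow-up.

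**6. With 20% loss (71 per arm).** The critical differences rise to 0.329 SD (one visit) and 0.285 SD (mean of both). At one visit, biases of 0.1 and 0.2 SD then give 9% and 22%.

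**The case against.** A reader might infer that follow-up is in fact carried out by people who know the allocation. The documents do not say so. Section 2.7 names the project leader only for opening envelopes, section 2.4 describes the team's part in the messages and not in outcome assessment, and no assessor is named anywhere. The gap is one of specification, and if duties are already separated, one sentence closes it.

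A reader might also infer that a modest assessor effect would by itself be likely to produce a significant result. The figures do not support that. At 0.1 SD about nine trials in ten, and at 0.2 SD about three in four, would still be non-significant on a one-visit comparison. An even chance needs 0.25 to 0.29 SD, which is half to 60% of the planned d = 0.50 (0.254/0.50 = 51%; 0.294/0.50 = 59%).

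The third objection is that the scales, including the quality-of-life score on which section 2.3 is based, are the patients' own fixed-response answers. Patients know whether they receive messages. Their own response bias may be a main route, and masking the interviewer does not remove it. This stands: masking helps most for wound area and only partly for the scales.

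Finally, the documents give no team size, so it cannot be taken for granted that duties can be split. That also stands and limits what the fix may ask. None of these points supplies the missing safeguard, and none justifies revealing allocation before baseline.

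**Conclusion.** The point holds as a gap in the plan: assessors are unnamed, masking is not specified, nothing prevents unmasked assessment, and allocation is revealed before baseline. The exposure is clearest for the 50% wound outcome and smaller for the interview scales.

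Its size can only be illustrated. With no true effect, false positives rise from 5% to about 10% at a bias of 0.1 SD and about 27% at 0.2 SD for one visit (12% and 34% on the mean of both post-tests with ρ = 0.5). For wounds, a net 13 or 14 of 89 reclassified is enough for significance. These figures rest on 1:1 allocation, no loss and assumed bias sizes. The documents give no SD, no control wound rate and no size for an assessor effect, so the figures show vulnerability and not actual bias. The change is worth making because it is cheap and because no analysis can remove such a bias afterwards.

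**What to change.** In section 2.7:
1. Complete the baseline questionnaires and wound measurement before the envelope is opened.
2. State that team members who open envelopes, select messages or contact intervention patients do not make the week-4 and week-8 wound measurements or, where the existing team allows, conduct the interviews. If the interviews cannot be separated, say so.
3. State that the assessor has no access to the allocation list, that patients are asked not to mention messages, and that any unmasking is recorded.
4. Acknowledge participant response bias on the self-report scales as a limitation that this does not remove.

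The cost is protocol wording and less freedom in deciding who covers which clinic visit. Masking of interviews will be imperfect. Sample size, endpoints and the intervention do not change. Recruitment is planned to July 2026 (section 2.2), and patients already assessed cannot be interviewed again under masking, so the change is worth more the sooner it is made.

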## 2.8 Data analysis

The data will be analyzed with SPSS statistical software for Windows 20.0 (SPSS, Inc., Chicago, IL, USA). The chi-square and Mann-Whitney U tests will be used to determine the homogeneity between the intervention and control groups. An intention-to-treat analysis approach (ITT) will be used. Generalized estimating equations (GEEs) will be used to examine the effects of intervention measures on improving the study subjects' self-care behavior, self-efficacy, and quality of life. The chi-square test will be used to detect whether there was any difference in the proportion of wounds reduced by 50% or more between the two groups of study subjects four weeks after admission.

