## 2. METHODS

### 2.1 Study design

A customized standardized patient education module will be developed and evaluated. A randomized controlled study design will be adopted.

Participants will be assigned to two parallel groups for the duration of the study.

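### Significance tests cannot show that the randomised arms are alike, and the GEEs give the baseline scores no stated role as covariates

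*Combined protocol and SAP*

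**What the plan says.** Section 2.1 states that "A randomized controlled study design will be adopted". Section 2.7 adds blocks of four within strata: "This study adopted categorical random allocation, with four categories", formed by crossing neuropathic ulcer (yes/no) with hemodialysis (yes/no). After consent the envelope is opened. Baseline questionnaires and wound measurement follow, with post-tests at weeks 4 and 8.

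Section 2.8 then says "The chi-square and Mann-Whitney U tests will be used to determine the homogeneity between the intervention and control groups". It does not list the variables to be tested, a significance level for these tests, or what follows from a significant result. For the outcomes it says "Generalized estimating equations (GEEs) will be used to examine the effects of intervention measures" on self-care behaviour, self-efficacy and quality of life. It names no covariates, no group-by-time term, and no role for the baseline score or the stratification factors. Section 2.3 counts three repeated measurements. With only two post-tests, baseline appears to be one of the GEE's outcomes.

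**The concern.** A significance test asks whether a gap is larger than chance would usually produce. In properly randomised arms that is not the useful question. A non-significant result does not show similarity, and a significant one is expected now and then by chance. What matters for the treatment comparison is the size of the gap and how strongly the variable predicts the outcome. Tests on the two stratification factors say little, because the allocation already balances them.

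The homogeneity tests are the only handling of baseline imbalance that the plan describes. Every score is measured at baseline, yet none is pre-specified as a covariate. At stake are precision that the trial has already paid for, and protection against a chance gap in the outcome score itself.

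**Working it through.** **Inputs.** N = 178 and three measurements (section 2.3). "We set the effect amount as 0.25", which for two groups is d = 2 × 0.25 = 0.5 SD. "the statistical power as 0.95" and "the alpha value as 0.05". Assumed, because the plan does not state them: 1:1 allocation (89 per arm), two-sided testing, no loss to follow-up, and the correlation r between baseline and follow-up scores, shown over a range.

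**The plan's own figure.** For a repeated-measures between-groups F test, λ = N·f²·m/(1 + (m − 1)ρ), with ρ the correlation among the repeated measurements. With f = 0.25, m = 3 and ρ = 0.5, N = 142 gives λ = 13.31 and power 95.2%. The stated 178 needs an unstated ρ of about 0.76–0.77, or unstated attrition of 20% (142/0.8 = 177.5). The point here does not depend on this, so 178 is taken as given.

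**What the tests can see.**
- Smallest significant gap: 1.96 × √(2/89) = 0.294 SD. This uses a normal-theory test; a rank test on normal data needs slightly more.
- Chance of a gap of at least 0.2 SD under sound randomisation: 2 × [1 − Φ(0.2/√(2/89))] = 18%. Those below 0.29 SD all pass as non-significant.
- Chance of at least one significant result among k independent baseline variables: 1 − 0.95^k = 23%, 40% and 54% for k = 5, 10 and 15. The plan does not give k.

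**What a baseline gap g does.** It shifts a follow-up-only difference by r·g and a change-from-baseline difference by −(1 − r)·g. At g = 0.29 and r = 0.5 these are +0.145 and −0.145 SD. Adjustment for the baseline score removes this shift on average.

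**Power at one follow-up visit, d = 0.5.** The variance factor v is 1 for follow-up only, 2(1 − r) for change, and 1 − r² for baseline-adjusted. The noncentrality is d/√(4v/N), with 176 df. The adjusted analysis uses 175 df and multiplies the variance by 1 + 1/173. Example at r = 0.5: unadjusted 0.5/√(4/178) = 3.34; adjusted 0.5/√(0.75 × 4/178 × 1.0058) = 3.84.

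| r | Follow-up only | Change | Baseline-adjusted |
|---|---|---|---|
| 0 | 91.3% | 65.0% | 91.1% |
| 0.3 | 91.3% | 80.1% | 93.4% |
| 0.5 | 91.3% | 91.3% | 96.9% |
| 0.6 | 91.3% | 96.0% | 98.5% |
| 0.7 | 91.3% | 99.0% | 99.6% |

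A normal approximation gives 93.8% for the adjusted analysis at r = 0.3. Adjustment breaks even with follow-up only near r = 0.08; at r = 0 it costs about 0.15 points. At r = 0.5 the adjusted variance is 0.75 of the unadjusted, so 0.75 × 178 = 133.5 patients would give the precision of 178 unadjusted.

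**Sensitivity.** For d = 0.3 and r = 0.5, power rises from 51% (either comparator) to 63%. If the two visits are averaged, with all pairwise correlations 0.5 and d = 0.5, the normal approximation gives 97.1% (either comparator) against 99.7%, so the gain is smaller.

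**The case against.** The strongest reply is that baseline testing is a common reporting habit and the plan attaches no consequence to it. That stands. A reader might infer that the tests decide which covariates enter the GEE, but section 2.8 does not say so. Harm from an adjust-only-if-significant rule therefore cannot be charged to this plan.

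A reader might also infer a raised type I error. Without an effect, unadjusted error is about 10–12% (r = 0.5 to 0.6) in trials whose baseline gap has |t| between 1.5 and the significance limit. Only about 8–9% of trials fall in that band, and overall the error is 5%.

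Next, baseline is apparently already one of three GEE measurements. If the effect is read from group-by-time, the gap is already subtracted, though over-corrected, and change is the nearer comparator. The gain is then large at low r (80% to 93% at r = 0.3) and under one point at r = 0.7.

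Finally, it is tempting to say that any baseline difference here must be chance. Section 2.7 does not secure that. The envelope is opened before baseline data are collected, so self-reported scores could reflect knowledge of the arm. This does not rescue the tests, which cannot separate that from chance. It does limit adjustment too: a score taken after allocation is known is not guaranteed to be a pre-randomisation covariate.

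**Conclusion.** The concern holds in limited form. The tests cannot do what section 2.8 asks of them, and baseline scores that are already collected have no stated covariate role. The trial is not invalid as planned. The loss is precision and exposure to chance imbalance: about 6 power points at one visit for d = 0.5 and r = 0.5, less against follow-up only at low r, and less against change at high r. Sizes rest on 1:1 allocation, 89 per arm analysed, and an assumed r. Repeated scores on the same scale would be expected to correlate well above the break-even of 0.08, but that is also an assumption.

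Adjustment should not be described as removing chance imbalance in general. It removes, on average, the linear effect of imbalance in that one score and leaves other prognostic factors untouched.

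**What to change.** Replace the homogeneity sentence in section 2.8 and complete the GEE specification, for example:

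> Baseline characteristics will be described by arm without significance tests. Each GEE will model the week-4 and week-8 scores, with the baseline value of the same score, neuropathic ulcer status and hemodialysis status as covariates fixed in advance, whatever baseline differences are observed. Baseline will not also be an outcome in the model. The adjusted difference between arms will be reported with its 95% confidence interval.

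In section 2.7, complete the baseline questionnaires and wound measurement before the envelope is opened. For patients already enrolled, state in the report that baseline self-reports may reflect known allocation.

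The cost is SAP wording, a change in the order of two steps at enrolment, a trivial loss of degrees of freedom, and a simple rule for missing baseline scores (for example the stratum mean). No new data are needed.

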## 2.2 Study setting and participants

The participants will be recruited from August 2023 to July 2026 and followed up for eight weeks at a medical center in northern Taiwan.

Recruited criteria were: (1) outpatients with DFUs over 20 years old; (2) can be interviewed in Mandarin or Taiwanese.

The exclusion criteria were: patients (1) planning to return visits within eight weeks less than two times; (2) without using a smartphone; (3) being unable to read text messages on a mobile phone or with impaired hearing; (4) with impaired fine hand movements; (5) unwilling to use the communication software LINE to receive text messages.

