### 2.6.2 Whether the Wound Shrinks

This study will measure the wound size at baseline, four and eight weeks. Then, whether the wound has shrunk will be determined by subtracting the pre-measurement area from the post-measurement area.

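### Section 2.8 promises intention-to-treat but gives no working correlation and no method for missed visits or unmeasured week-4 wounds, so the comparison can be biased if missingness relates to outcome differently by arm

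*Combined protocol and SAP*

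**What the plan says.** The analysis principle is one sentence in section 2.8: "An intention-to-treat analysis approach (ITT) will be used". For self-care behavior, self-efficacy and quality of life, "Generalized estimating equations (GEEs) will be used to examine the effects of intervention measures". For the wound, "The chi-square test will be used to detect whether there was any difference in the proportion of wounds reduced by 50% or more", compared between arms at four weeks.

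The data come from repeated contact. Section 2.6.2 states "This study will measure the wound size at baseline, four and eight weeks", and section 2.7 says the two post-tests "will be conducted four and eight weeks after baseline data collection". Section 2.7 also puts allocation before baseline: "the project leader will open envelopes to arrange their group location. Then, the data collection begins".

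No section defines the intention-to-treat set, names a GEE working correlation, gives an expected dropout rate, says how a missed questionnaire or an unmeasured week-4 wound is handled, or plans a sensitivity analysis.

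**The concern.** Intention-to-treat analysis needs a rule for patients whose outcome is not observed. Without one, the named methods fall back on what was recorded. GEE leaves out missed visits, and the chi-square leaves out anyone without a week-4 measurement. A patient lost between opening of the envelope and baseline contributes to neither.

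Standard GEE is consistent whatever the working correlation only when visits are missing completely at random. That is doubtful here. Participants are outpatients, and fast healing or deterioration could each be a reason not to return. One arm receives tailored messages and the other routine care, and no blinding is described, so the reasons for missing a visit could differ by arm. At stake are the estimated effects on the scales, the wound comparison and the 5% error rate of both tests.

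**Working it through.** **Inputs.** From the documents: 178 patients (2.3), two groups (2.1), three measurements (2.3), alpha 0.05 (2.3). The allocation ratio is not stated; 1:1 is assumed, giving 178/2 = 89 per arm. The plan gives no dropout or bias figure to reproduce. Assumed: between-visit correlation 0.6; 20% missing at week 8 with log-odds of 1 per SD of the week-4 score; no true effect.

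**Step 1: bias of independence GEE at week 8.** With group, time and their interaction in the model, the week-8 contrast is the difference in observed week-8 means less the baseline difference. If p(X) is the chance of missing week 8 given a standard normal week-4 score X, the mean of X among those who stay shifts by E[p(1−p)]/0.80 in absolute size.
- Integrating the logistic curve that averages 20% gives E[p(1−p)] = 0.139, so the shift is 0.139/0.80 = 0.173 SD.
- Pattern in one arm only: bias = 0.6 × 0.173 = 0.10 SD.
- Opposite directions by arm: 2 × 0.104 = 0.21 SD.
- Same mechanism in both arms: the shifts cancel and the bias is 0.

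**Step 2: type I error.** With 20% missing in each arm, 89 × 0.80 = 71.2 are seen at week 8.
- Variance per arm = 1/71.2 + 1/89 − 2(0.6)/89 = 0.01404 + 0.01124 − 0.01348 = 0.0118.
- Standard error of the contrast = √(2 × 0.0118) = 0.154.
- Rejection rate = 1 − Φ(1.96 − bias/SE) + Φ(−1.96 − bias/SE): 10% at 0.10 SD, 11% at 0.11, 22% at 0.18, 30% at 0.22.

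**Step 3: simulation under the same assumptions**, run several times independently (400 to 1,500 trials per scenario where the number is recorded):

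| Method and pattern | Bias (SD) | Type I error |
|---|---|---|
| Independence GEE, one arm only | 0.10-0.11 | 8-11% |
| Independence GEE, opposite directions | 0.18-0.22 | 22-32% |
| Exchangeable GEE, correctly specified | about 0 to 0.01 | 4-6% |
| Unstructured mixed model | under 0.01 | about 6% |

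If the 0.25 in section 2.3 is Cohen's f, it corresponds to d = 0.5 for two groups. Biases of 0.10 and 0.22 SD are then 20% and 44% of the effect planned for.

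**Step 4: missingness that depends on the unseen outcome.** With correlation 0.5 and outcome-related dropout in the intervention arm only, exchangeable GEE was biased by −0.15 SD with type I error about 16% (400 trials). All 178 patients stayed in the model. Missing-at-random methods do not cure this case.

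**Step 5: wound test on measured wounds only.** Assume a true rate of 40% in both arms and 10% of responders unmeasured in both.
- Non-responders unmeasured 30% in the intervention arm, 10% in control: 0.36/(0.36 + 0.42) = 46.2% against 0.36/(0.36 + 0.54) = 40.0%. The spurious difference is 6 points and type I error about 12%.
- Non-responders unmeasured 40% and 10%: 0.36/(0.36 + 0.36) = 50% against 40%. The spurious difference is 10 points and type I error about 23%.
- Non-responders unmeasured 30% in both arms: 46.2% in both, difference 0, type I error 5%.

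**Step 6: counting a missing wound as not reduced.** With purely random loss of 10% in one arm and 20% in the other, a true 40% gives 0.40 × 0.90 = 36% against 0.40 × 0.80 = 32%, a spurious 4 points (5 points at a true 50%). If 25% of responders and 10% of non-responders are unmeasured, measured wounds give 0.30/(0.30 + 0.54) = 35.7%, while missing-as-not-reduced gives 0.40 × 0.75 = 30%, further from 40%.

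**The case against.** The strongest reply is that the plan is silent rather than wrong. It never says that GEE will be restricted to available cases or that unmeasured wounds will be excluded. A chi-square test can include every randomised patient once missing wounds have a rule. GEE does not discard patients who miss a follow-up: anyone with a baseline record stays in the model and only the missed visit is lost, as in a mixed model. The larger biases also depend on an independence working correlation that the plan does not choose; naming a suitable one would remove most of the bias in that scenario. Follow-up lasts only eight weeks, and section 2.2 excludes patients planning fewer than two return visits in that time, so losses may be modest.

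Most of this stands, and it rules out some stronger readings. A reader might infer that the plan has chosen an available-case analysis, or that GEE drops randomised patients wholesale; the text supports neither. A reader might also take a true 40% response appearing as 36% for a biased comparison, but that is distortion within one arm and cancels if both arms share it.

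The reply does not close the gap. Leaving the working correlation open leaves type I error anywhere from about 5% to about 30% on the same data, and the intention-to-treat label supplies no rule for the unmeasured wound.

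**Conclusion.** The point holds as a gap with a concrete remedy. The stated methods do not deliver the promised intention-to-treat analysis once visits are missed, and the comparison can be biased. It would be too strong to say that outcome-related dropout does bias it: in the no-effect scenarios examined, harm appeared only when the mechanism differed between arms. The documents give no dropout data to show that it will, and nothing in them supports the opposite-directions pattern in particular.

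The plausible size is about 0.1 SD on a scale if one arm is affected, about 0.2 SD in the extreme pattern, and 6 to 10 percentage points on the wound outcome in the differential-loss examples. The dropout rates, the correlation, the response rates and the 1:1 ratio are all assumptions. The change should be made before outcome data are examined.

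**What to change.** In section 2.8, define the analysis set as all randomised patients in their allocated arm, and say how those lost before baseline are counted. Then choose one of these for the scales:

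- a likelihood-based repeated-measures mixed model with unstructured covariance; or
- GEE on data multiply imputed separately by arm from baseline and observed scores, wound area and the stratification factors, with a stated working correlation other than independence.

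Analyse the 50% wound-reduction outcome in all randomised patients using the same imputation. Keep missing-as-not-reduced as a sensitivity analysis only, given step 6.

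The cost is a few sentences and some programming, with no extra patients or data. The analysis and its reporting become somewhat more complex. Both options rest on missing-at-random, so they lower the risk of bias but cannot exclude it.

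### Randomisation is stratified by neuropathic ulcer and hemodialysis, but the week-4 wound comparison is a chi-square that does not use the strata: valid, but conservative if the strata predict healing

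*Combined protocol and SAP*

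**What the plan says.** Section 2.7 (Data collection) describes stratified allocation: "we will perform block randomization of four categories", with a block size of four. It then lists the categories: "This study adopted categorical random allocation, with four categories", namely neuropathic ulcer yes or no, crossed with hemodialysis yes or no.

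Section 2.8 (Data analysis) does not mention these categories. For the wound outcome at week 4 it says: "The chi-square test will be used to detect whether there was any difference in the proportion of wounds reduced by 50% or more". For the questionnaire outcomes it says: "Generalized estimating equations (GEEs) will be used to examine the effects of intervention measures on improving the study" (the sentence goes on to name self-care behavior, self-efficacy and quality of life). No model terms, covariates, baseline handling or working correlation are given there or elsewhere.

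Two further passages bear on the GEEs. Section 2.3 sets "the number of repeated measurements as 3", which matches baseline plus the two post-tests that "will be conducted four and eight weeks after baseline data collection" (section 2.7). On the order of steps, section 2.7 says: "the project leader will open envelopes to arrange their group location. Then, the data collection begins".

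**The concern.** Blocking within strata forces the arms to be nearly balanced on neuropathy and hemodialysis. If these factors predict healing, balance removes part of the chance variation in the difference between arms. An ordinary chi-square computes its standard error as if that variation were still there. The error is on the safe side, but a real effect on wound reduction is more likely to be missed, although each patient's stratum is known before the envelope is opened.

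For the GEEs the gap is one of specification. Precision at week 8 depends on whether baseline is a covariate, an outcome or unused, and the plan does not say. Because baseline questionnaires follow the opening of the envelope, self-reported baseline values could react to allocation, and this limits how cleanly they can be used for adjustment.

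**Working it through.** **The plan's own figure.** Section 2.3 gives N = 178 for quality of life (effect 0.25, power 0.95, alpha 0.05, three measurements). Reading 0.25 as Cohen's f, the between-groups repeated-measures F test has noncentrality f²·N·m/(1+(m−1)ρ). With ρ = 0.5, N = 142 suffices: 0.0625 × 142 × 3/2 = 13.3, power 95.2%. Then 142/(1 − 0.20) = 177.5, rounded up to 178. Alternatively, ρ of about 0.77 with no dropout also gives 178. The documents state neither a correlation nor a dropout rate, so 178 can be neither confirmed nor called wrong. No power figure is attached to the wound test. Below, 142 serves only as an illustrative lower number analysed.

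**Wound test: assumptions.** From the documents: four strata, blocks of four, N = 178, alpha 0.05. Assumed: 1:1 allocation, two-sided testing, stratum shares 15/45/10/30%, and control success rates of
- strong: 25/60/10/40%
- mild: 35/50/25/45%
- none: 44% throughout.

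**Why the chi-square is conservative.** Under no effect, the chi-square uses the variance p̄(1−p̄). With the strata balanced, the relevant variance is Σ w·p(1−p), summed over strata with share w.
- Strong: p̄ = 0.15×0.25 + 0.45×0.60 + 0.10×0.10 + 0.30×0.40 = 0.4375, so p̄(1−p̄) = 0.2461. Within strata: 0.0281 + 0.1080 + 0.0090 + 0.0720 = 0.2171. Ratio 0.882. The effective critical value is 1.96/√0.882 = 2.087, a type I error of about 3.7%.
- Mild: within strata 0.0341 + 0.1125 + 0.0188 + 0.0743 = 0.2396; ratio 0.974; type I error about 4.7%.
- None: ratio 1; type I error 5%.

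**Simulated type I error and power** (N = 178, 40,000 trials per cell; CMH = Cochran-Mantel-Haenszel over the four strata):

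| Strata | Odds ratio | Chi-square | CMH, uncorrected | Logistic, main effects | CMH, continuity-corrected |
|---|---|---|---|---|---|
| Strong | 1 | 3.8% | 5.0% | 5.1% | 3.4% |
| Strong | 2.0 | 50.0% | 56.8% | 57.0% | 50.2% |
| Strong | 2.5 | 75.6% | 80.5% | 80.7% | 75.5% |
| Mild | 1 | 4.9% | 5.2% | 5.3% | 3.6% |
| Mild | 2.0 | 60.2% | 62.1% | 62.5% | 56.2% |
| Mild | 2.5 | 83.5% | 84.5% | 84.8% | 80.5% |
| None | 1 | 5.0% | 4.9% | 5.0% | 3.4% |
| None | 2.0 | 62.5% | 62.5% | 63.1% | 56.8% |
| None | 2.5 | 85.0% | 84.7% | 85.1% | 80.7% |

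The chi-square loses 5 to 7 points with strong strata and 1 to 2 with mild strata. The continuity-corrected CMH cancels the gain with strong strata and does worse than the chi-square otherwise.

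**142 analysed**, chi-square against uncorrected CMH: strong 44 vs 48% (odds ratio 2.0) and 67 vs 71% (2.5); mild 52.4 vs 52.7% and 74.8 vs 75.0%.

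**Other assumed rates**, N = 178, odds ratio 2.4: 75.3 vs 78.8% with control rates 25/55/15/45%, and 64.9 vs 73.2% with 15/65/10/45%. The pattern is the same; the size depends on how far apart the strata are.

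**GEE, week-8 contrast.** Assumed: 89 per arm, complete data, equal correlation ρ between visits, and an effect of 0.5 SD (equal to f = 0.25 for two groups). Per-arm variance v, in units of the outcome variance, is 2(1−ρ) with a free baseline difference, 1 for follow-up only, and 1−ρ² with baseline as covariate. The noncentrality is 0.5/√(2v/89). At ρ = 0.3 it is 0.5/√(2×1.40/89) = 2.82 for the first and 0.5/√(2×0.91/89) = 3.50 for the last.

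| Model | Power at ρ = 0.3 | ρ = 0.5 | ρ = 0.7 |
|---|---|---|---|
| Free baseline difference | 80% | 91% | 99.0% |
| Follow-up only | 91% | 91% | 91% |
| Baseline as covariate | 94% | 97% | 99.6% |

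Adding the strata helps little here: if they explain an assumed 10% of outcome variance, the baseline-adjusted variance falls a further 6/4/2%.

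**If baseline reacts to allocation.** For an assumed shift of 0.1 SD, the bias is 0.10 SD with a free baseline difference, ρ × 0.1 = 0.03/0.05/0.07 SD with baseline as covariate, and 0 for follow-up only.

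**The case against.** The strongest reply is that this is advice on efficiency. An unstratified chi-square after stratified randomisation is a legitimate choice, and section 2.8 says only chi-square, so that it ignores the strata is inferred from silence. The largest loss needs control success rates running from 10% to 60% across strata, and nothing in the documents says so. Section 2.3 sizes the trial on quality of life, so no stated power for the wound test is missed. With fewer patients analysed, the gain shrinks. All of this stands, and it limits the size of the point. It does not remove it: the adjusted test uses information already recorded and costs almost nothing if the strata turn out not to matter.

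A second reply is that adjusting for baseline fits poorly with a warning that baseline may react to allocation. This stands in part. Section 2.7 does not say whether patients or interviewers know the group when the baseline questionnaire is given, so a reaction is a possibility, not a finding. It is why adjustment should be tied to collecting baseline first, with an unadjusted analysis alongside.

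Three stronger readings are tempting, and the documents support none of them. A reader might infer that ignoring the strata inflates false positives; the calculation shows the reverse. A reader might infer that the GEEs lose power; section 2.8 gives no terms, so a loss is possible but not shown. A reader might infer from the recruitment window in section 2.2 (August 2023 to July 2026) that patients are already enrolled; it is a planned window and does not report enrolment.

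**Conclusion.** The point holds as one of precision and specification, not validity. The strata used to randomise should also be used in the week-4 wound analysis. The benefit ranges from nil to about 7 power points at N = 178 and is smaller if fewer patients are analysed. It rests on assumed stratum shares, success rates and odds ratios. That the test is conservative when the strata are prognostic follows from the design; how prognostic they are is unknown.

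The GEE part is secondary and is mainly missing detail. At ρ = 0.3, the unstated choice of model moves week-8 power between 80% and 94% for a 0.5 SD effect; at ρ = 0.7, the range is 91% to 99.6%. This is worth settling in writing before outcomes are examined by group. The change should be made, but the trial's conclusions would not be unsound without it.

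**What to change.** **Wound outcome.** In section 2.8, replace the chi-square by logistic regression of the week-4 outcome (reduction of 50% or more) on group, with neuropathic ulcer and hemodialysis as main effects. An uncorrected CMH test over the four strata has equivalent power and could be named instead; the continuity-corrected version should not be used. Logistic regression is the simpler choice if a stratum is very small, and it avoids having to specify which CMH statistic is read from the output. The downside is that the odds ratio is conditional on the strata, so the crude proportions by arm should be shown beside it.

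**GEEs.** For each outcome, state: weeks 4 and 8 as outcomes; group, visit and group-by-visit terms; the baseline value; the two stratification factors; and the working correlation.

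**Order of steps.** In section 2.7, collect baseline before the envelope is opened for any patient still to be enrolled. For any patient enrolled under the current order, add a sensitivity analysis of weeks 4 and 8 without baseline adjustment (group, visit, group-by-visit and the two factors). If applied to all 178 patients, it has 91% power for 0.5 SD.

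**Cost.** The analysis changes are wording only, since stratum and baseline values are already to be recorded. If the strata are not prognostic, the power cost for the wound test is about 0.3 points or less (85.0 vs 84.7% for the uncorrected CMH, and no loss seen for logistic regression). Collecting baseline first swaps two steps at enrolment.
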